17.11. Use of Information and Publication

All information, including but not limited to information regarding JNJ-54861911 or the sponsor's operations (e.g., patent application, formulas, manufacturing processes, basic scientific data, prior clinical data, formulation information) supplied by the sponsor to the investigator and not previously published, and any data, including exploratory biomarker research data, generated as a result of this study, are considered confidential and remain the sole property of the sponsor. The investigator agrees to maintain this information in confidence and use this information only to accomplish this study, and will not use it for other purposes without the sponsor's prior written consent.

The investigator understands that the information developed in the study will be used by the sponsor in connection with the continued development of JNJ-54861911, and thus may be disclosed as required to other clinical investigators or regulatory agencies. To permit the information derived from the clinical studies to be used, the investigator is obligated to provide the sponsor with all data obtained in the study.

The results of the study will be reported in a Clinical Study Report generated by the sponsor and will contain CRF data from all study sites that participated in the study, and direct transmission of clinical laboratory data from a central laboratory into the sponsor's database. Recruitment performance or specific expertise related to the nature and the key assessment parameters of the study will be used to determine a coordinating investigator. Results of pharmacogenomic or exploratory biomarker analyses performed after the Clinical Study Report has been issued will be reported in a separate report and will not require a revision of the Clinical Study Report. Study subject identifiers will not be used in publication of results. Any work created in connection with performance of the study and contained in the data that can benefit from copyright protection (except any publication by the investigator as provided for below) shall be the property of the sponsor as author and owner of copyright in such work.

Consistent with Good Publication Practices and International Committee of Medical Journal Editors guidelines, the sponsor shall have the right to publish such primary (multicenter) data and information without approval from the investigator. The investigator has the right to publish study site-specific data after the primary data are published. If an investigator wishes to publish information from the study, a copy of the manuscript must be provided to the sponsor for review at least 60 days before submission for publication or presentation. Expedited reviews will be arranged for abstracts, poster presentations, or other materials. If requested by the sponsor in writing, the investigator will withhold such publication for up to an additional 60 days to allow for filing of a patent application. In the event that issues arise regarding scientific integrity or regulatory compliance, the sponsor will review these issues with the investigator. The sponsor will not mandate modifications to scientific content and does not have the right to suppress information. For multicenter study designs and substudy approaches, secondary results generally should not be published before the primary endpoints of a study have been published. Similarly,

investigators will recognize the integrity of a multicenter study by not submitting for publication data derived from the individual study site until the combined results from the completed study have been submitted for publication, within 12 months of the availability of the final data (tables, listings, graphs), or the sponsor confirms there will be no multicenter study publication. Authorship of publications resulting from this study will be based on the guidelines on authorship, such as those described in the Uniform Requirements for Manuscripts Submitted to Biomedical Journals, which state that the named authors must have made a significant contribution to the design of the study or analysis and interpretation of the data, provided critical review of the paper, and given final approval of the final version.

Registration of Clinical Studies and Disclosure of Results

The sponsor will register and/or disclose the existence of and the results of clinical studies as required by law.

REFERENCES

Attachment 1: Evaluation of Increased Liver Enzymes

The following process should be followed whenever per protocol assessments for a given subject indicate an elevation of alanine aminotransferase (ALT) or aspartate aminotransferase (AST) $\geq 3\times$ upper limit of normal (ULN):

1. Initial Investigation

Within 24 to 72 hours of receipt of abnormal laboratory results, the investigator and study site are to perform the following:

- a. Repeat blood sampling:
 - Chemistry (include amylase if subject has abdominal pain or vomiting)
 - Complete hematology with eosinophil count
 - International normalized ratio (INR)
 - Hepatitis serology:
 - Hepatitis A: anti HAV IgG, anti HAV IgM
 - Hepatitis B : HBsAg, anti-HBc, anti-HBs
 - Hepatitis C: anti-HCV
 - Hepatitis E: anti-HEV IgG and IgM
 - Epstein Barr virus (EBV): anti-VCA IgG and IgM, anti-EBNA IgG
 - CMV: anti-CMV IgG and IgM.)
 - Anti-nuclear antibody (ANA)
 - One 5 mL sample of plasma for exploratory studies to evaluate the potential cause or risk factors for drug-related liver injury.
- b. Collect detailed history of present illness and additional medical history, to include:
 - Recent abdominal pain, pruritis, rash
 - Prior abnormal liver tests, liver disease, exposure to hepatotoxins, diabetes, obesity, marked hypertriglyceridemia, gallstone disease or family history of gallstone or liver disease
 - Record alcohol use, other medications including acetaminophen, nonsteroidal anti-inflammatory drugs and over-the-counter herbal, vitamin, special diets, or nutritional supplements; any recent change in prescription drugs with start and stop dates; exposure to environmental chemical agents, or recreational drug use.
- c. Perform a full physical exam, with specific comments on:
 - Palpable liver, size, tenderness
 - Palpable spleen, size, tenderness
 - Jaundice
 - Stigmata of chronic liver disease: spider angiomas, gynecomastia, palmar erythema, testicular atrophy

d. Schedule mandatory hepatic/pancreatic ultrasound

2. Follow-up Blood Sampling and Ongoing Contact with Medical Monitor

After the initial investigation, regardless of results, serum chemistry is to be performed (using the central lab retest kit) per the schedule below (Table 1) and close contact with the medical monitor with a minimal contact frequency (as outlined in the table) is also expected.

Table 1: Minimum Schedule for Follow-Up Blood Sampling and Contact with Medical Monitor

	AST or ALT Levels From Most Recent Laboratory Values			
	$\geq 5 \times \text{ULN}$	$\geq 3, < 5 \times \text{ULN}$	$> 1, < 3 \times \text{ULN}$	WNL
Blood sampling frequency	2× per week	1× per week	Once every 2 weeks until sponsor approves reduction to 1× per month	1× per month until 3 consecutive months within normal limits, then Resume the standard, per protocol schedule
Frequency of site contact with medical monitor	1× per week	1 x per week	1× per month	Once, just prior to resumption of the standard, per protocol schedule
Abbreviations: ALT=alanine aminotransferase, AST=aspartate aminotransferase; ULN=upper limit of normal; WNL=within normal limits				

3. Hepatology/Gastroenterology Consult

Mandatory, urgent hepatology/gastroenterology consult must be conducted if any of the following occurs:

- AST or ALT $\geq 8 \times \text{ULN}$
- AST or ALT $\geq 3 \times \text{ULN}$ with symptoms
- AST or ALT $\geq 3 \times \text{ULN}$ and total bilirubin $\geq 2 \text{ mg/dL}$
- AST or ALT $\geq 5 \times \text{ULN}$ persists for > 1 week
- AST or ALT $\geq 3 \times \text{ULN}$ persists for > 2 weeks

4. Discontinuation of Study Treatment:

Between Weeks 52 and 64, treatment must be discontinued if any of the following occurs:

- ALT or AST $> 5 \times \text{ULN}$
- ALT or AST $> 3 \times \text{ULN}$ and total bilirubin $> 2 \times \text{ULN}$ or INR > 1.5
- ALT or AST $> 3 \times \text{ULN}$ with the appearance of fatigue, nausea, vomiting, right upper quadrant pain or tenderness, fever, rash, and/or eosinophilia $> 5\%$

After Week 64, treatment must be discontinued if any of the following occurs:

- ALT or AST $> 8 \times \text{ULN}$

- ALT or AST $> 5 \times$ ULN for more than 2 weeks
- ALT or AST $> 3 \times$ ULN and total bilirubin $> 2 \times$ ULN or INR > 1.5
- ALT or AST $> 3 \times$ ULN with the appearance of fatigue, nausea, vomiting, right upper quadrant pain or tenderness, fever, rash, and/or eosinophilia $> 5\%$

5. SAE Reporting

Subjects who meet the criteria for discontinuation of study treatment should have the event reported as an SAE and should follow the SAE reporting process as outlined in Section 12.3.2 of the protocol.

6. Continuation or Resumption of Study Treatment:

Study treatment may continue in asymptomatic subjects who do not meet the discontinuation rules, however, the investigator/site must adhere to the blood sampling and contact with Medical Monitor schedule in [Table 1](#).

For subjects resuming treatment after an interruption of less than 7 days, the blood sampling schedule in [Table 1](#) should be followed. In case treatment is resumed after interruption of more than 7 days, resumption of treatment must be discussed with and approved by the sponsor medical monitor. In these cases, follow-up blood sampling should occur weekly for the first month and thereafter [Table 1](#) should be followed. Dosages should be at the same level as before the interruption.

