To reduce the maximum possible theoretical risks associated with lumbar punctures including cerebral herniation (due to pre-existing intracranial hypertension) and spinal epidural hematoma with compression of the cauda equina, additional eligibility criteria and other preventive action

are put in place. Medical conditions contraindicating a lumbar puncture will be excluded. To reduce the risk of post-dural puncture headache (PDPH) caused by persistent CSF leakage, subjects are preferably placed on bed, rest in a supine position during sampling. To avoid the introduction of an infection into the CSF (which is a rare complication), lumbar puncture is performed under sterile conditions. Prior to the puncture, all subjects will be examined thoroughly for (possible) topical infections or local dermatological condition at the puncture site, of which their presence will lead to exclusion of the subject. All CSF collections will be performed under aseptic conditions. Irritation of nerve roots, possibly caused upon insertion of the needle is usually benign and self-limiting. The CSF puncture sites (L3-L4 or L4-L5) will prevent spinal cord trauma. Only experienced and qualified physicians are allowed to perform the applicable procedures. Coagulation tests at screening and an eye exam with fundoscopy are performed at screening to exclude intracranial hypertension.

The total blood volume to be collected will not exceed 450 mL annually, which is considered to be safe and acceptable in comparison to a Red Cross blood donation.

A placebo arm is necessary to allow for an accurate assessment of the safety and tolerability of the study drug; the use of placebo over the 6 month treatment period in the parent study, 54861911ALZ2002, and in the first 12 months of this study, extends this assessment into the longer term. Since there is, at this moment, no treatment available for subjects at risk for AD or subjects in the earliest AD spectrum, the use of placebo is warranted. Throughout the course of the study, the Sponsor will have the option based on recommendations by the Data Review Committee, or based upon newly emerging safety, biomarker or efficacy data from ongoing or completed JNJ-54861911 studies, to revise the dose levels in this study.

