Specific dermatologic and ophthalmologic examinations, as described in Section 9.2, Safety Evaluations have been implemented in this study as potential BACE1- or BACE2-linked toxicities (e.g. melanin deposition changes and retinal abnormalities) have been described in the literature (e.g. BACE1 or BACE2 knock-out mice). With the exception of fur discoloration resulting in progressive lightening of the fur from normal dark brown to paler cream or grey, which was seen in one species only (Tg mice in the 6 month carcinogenicity study), however, these toxicities have not been observed in nonclinical chronic studies with JNJ-54861911. Note that cases of lightening of skin, lightening of hair or ophthalmological adverse events are considered adverse events of special interest (AESI) and are subject to reporting timelines as described in Section 12.3.4.

As a result of the newly identified case of drug-induced hepatotoxicity, if at any time during treatment a subject has an ALT or AST result that is $\geq 3 \times$ ULN, the test should be repeated within 24 - 72 hours and, if confirmed, the further evaluation and management procedures described in [Attachment 1](#) should be followed.

In addition to the (safety) MRI assessments performed under the 54861911ALZ2002 study (if applicable), safety MRIs will be collected in this study during both DB and OL treatment periods, as indicated in the Time and Events Schedule, to monitor any treatment-emergent abnormalities including ARIA-edema or effusion (E) and ARIA-hemosiderin (H). Additional annual MRIs will be collected in OL period. If any safety related changes are observed (e.g. ARIA-E), additional safety MRIs may be collected at a frequency recommended by the DRC.

In case of any changes observed in any of the safety measures performed that are considered not clinically significant or do not have a direct clinical symptomatology as assessed by the investigator, they should be closely monitored, with a potential increased safety monitoring frequency as deemed appropriate by the investigator. In addition, these findings will be presented to the DRC, who will make recommendations regarding the safety and continuation of the study as per its charter.

Biomarker Collection

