3.4. Stopping Criteria

3.4.1. Individual Criteria for Stopping Study Treatment

In this Phase 2 study the following specific individual rules for stopping study treatment will apply (see Section 10.2 for details):

- A subject has a mean QTcF interval of >500 msec if confirmed upon repeat ECG, and/or mean QTcF increase versus baseline of >60 msec if confirmed upon repeat ECG, after consultation with the sponsor's medical monitor (all based on triplicate recordings).
- The investigator believes that for safety reasons (e.g., adverse event) it is in the best interest of the subject.
- Between Weeks 52 and 64, treatment must be discontinued if any of the following occurs:
 - ALT or AST $>5\times$ ULN
 - ALT or AST $>3\times$ ULN and total bilirubin $>2\times$ ULN or international normalized ratio (INR) >1.5
 - ALT or AST $>3\times$ ULN with the appearance of fatigue, nausea, vomiting, right upper quadrant pain or tenderness, fever, rash, and/or eosinophilia $>5\%$
- After Week 64, treatment must be discontinued if any of the following occurs:
 - ALT or AST $>8\times$ ULN
 - ALT or AST $>5\times$ ULN for more than 2 weeks
 - ALT or AST $>3\times$ ULN and total bilirubin $>2\times$ ULN or INR >1.5
 - ALT or AST $>3\times$ ULN with the appearance of fatigue, nausea, vomiting, right upper quadrant pain or tenderness, fever, rash, and/or eosinophilia $>5\%$
- A subject who meets any of the withdrawal criteria described in Section 10.3.

Events of elevated liver enzymes or increased QTc that require subjects to discontinue will be considered as serious and will be reported to Sponsor within 24 hours of the knowledge of the event.

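### From Week 52, follow-up liver draws order serum chemistry only, although INR and eosinophils can each force a stop at ALT/AST >3x ULN

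*Protocol*

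**What the plan says.** The numeric liver stop rules appear in Sections 3.4.1 and 10.2 and in Attachment 1, item 4. They cover two windows, Weeks 52-64 and after Week 64. Both windows require a stop at ALT/AST >3x ULN when INR exceeds 1.5. Both also require one at that enzyme level "with the appearance of fatigue, nausea, vomiting, right upper quadrant pain or tenderness, fever, rash, and/or eosinophilia" above 5%.

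Attachment 1 then sets out the handling of an elevation:

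- Item 1 is an initial investigation within 24 to 72 hours. It includes chemistry, hematology with an eosinophil count, INR, viral serology, a physical examination and an ultrasound.
- Item 2 governs what follows: "After the initial investigation, regardless of results, serum chemistry is to be performed (using the central lab retest kit) per the schedule below". Table 1 sets draws twice a week at >=5x ULN and weekly at >=3 to <5x ULN.
- Item 3 begins: "Mandatory, urgent hepatology/gastroenterology consult must be conducted if any of the following occurs". Its triggers include >=3x ULN lasting more than 2 weeks and >=5x ULN lasting more than 1 week.
- Item 6 says: "Study treatment may continue in asymptomatic subjects who do not meet the discontinuation rules", on condition that the site keeps to Table 1.

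Section 9.2.9 puts bilirubin in the chemistry panel and the white-cell differential in the hematology panel. INR is in none of the three panels. Elsewhere, coagulation testing is mentioned only in Section 1.2: "Coagulation tests at screening and an eye exam with fundoscopy are performed at screening to exclude intracranial hypertension".

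**The concern.** Item 6 keeps a subject on drug only while no stop rule is met, and relies on the Table 1 draws to watch for that. As item 2 orders them, those draws cannot show whether two of the rules have since been met. Bilirubin, which shares a bullet with INR, is rechecked every time; INR is not.

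A site that follows Attachment 1 to the letter could therefore leave a subject on drug after a mandatory stop threshold has been crossed. Such a stop is also a serious adverse event by rule (Section 12.3.2), so the report would be missed too. Section 12.3.5 already classes raised liver enzymes as an adverse drug reaction. What is at stake is the safety of individual subjects in the open-label phase.

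**Working it through.** The protocol states no figure to reproduce. The check compares the laboratory stop triggers with the tests ordered, then counts draws.

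**Triggers against tests (from Week 52, ALT/AST >3x ULN)**

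| Trigger | Item 1 work-up | Table 1 draw (item 2) | Scheduled visit |
|---|---|---|---|
| Bilirubin >2x ULN | yes | yes | yes |
| INR >1.5 | yes | not ordered | not ordered |
| Eosinophilia >5% | yes | not ordered | yes |

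**Follow-up draws before another safeguard applies.** Let day 0 be receipt of the abnormal result, with the work-up on day 1 to 3 and Table 1 draws after it.

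- Weekly: work-up day + 7 = day 8-10, then day 15-17. That is 1 draw by day 14.
- Twice weekly (every 3.5 days): work-up on day 1 gives 4.5, 8, 11.5, 15; work-up on day 3 gives 6.5, 10, 13.5, 17. Either way, 1 draw by day 7 and 3 by day 14.
- If persistence is counted from the repeat sample instead: weekly 7, 14 = 2 draws; every 3.5 days 3.5, 7 = 2 by day 7, and 3.5, 7, 10.5, 14 = 4 by day 14.

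So at 3 to <5x ULN, 1-2 draws precede the >2-week consult. At 5-8x ULN after Week 64, 1-2 precede the >1-week consult and 3-4 precede the stop for >5x ULN lasting more than 2 weeks. Item 2 orders INR on none of them. At 3 to <5x ULN, chemistry-only follow-up has no end date, even after the consult.

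**A subject staying at 3 to <5x ULN on weekly draws.** Scheduled hematology comes from the open-label Time and Events Schedule, footnotes t to w. With visits every k weeks, draws between visits = k - 1 and eosinophil readings per 12 weeks = 12/k.

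| Period | k | Draws between visits | Eosinophil readings per 12 weeks |
|---|---|---|---|
| Weeks 52-64 | 2 | 1 | 6 |
| Weeks 64-76 | 4 | 3 | 3 |
| Weeks 76-100 | 8 | 7 | 1.5 |
| After Week 100 | 12 | 11 | 1 |

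For INR, two readings are possible. If item 1 is done once per episode, there are 0 further INR tests on 12 weekly draws. If each scheduled visit at >=3x ULN restarts item 1, INR returns with those visits, and the gap is the third column.

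**How common the setting is.** Section 1.1 reports 11 subjects above 3x ULN among more than 200 given drug or placebo in studies longer than 1 month. That is below 11/200 = 5.5%, and none had related symptoms. Only some of these would remain on drug and later cross an INR or eosinophil threshold; the document gives no basis for that fraction.

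**The case against.** The strongest reply is that item 1 is not a single event. Attachment 1 applies "whenever per protocol assessments for a given subject indicate an elevation of alanine aminotransferase" or AST to >=3x ULN, and Section 3.2 calls for a repeat test "if at any time during treatment a subject has an ALT or AST result that is" at or above that level. Restarting item 1 at every Table 1 draw is implausible: it would repeat serology, examination and ultrasound weekly or twice weekly and leave item 2 without purpose. Restarting it at scheduled visits only is plausible, because Table 1 itself separates its draws from the standard schedule. That part stands. It makes the gap small in Weeks 52-64, the period with the closest monitoring, and leaves it largest after Week 100.

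Other safeguards are real. Table 1 is a floor, and Section 9.1.1 lets the physician add measurements. Section 9.2.9 allows local laboratories, and the investigator may stop drug for safety. Contact with the medical monitor is weekly at >=3x ULN, and a specialist consult is mandatory for persistent elevation. None of these orders a repeat INR or differential.

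A reader might infer three stronger things that the document does not support:

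- That a mandatory stop could be missed this way in the double-blind year. The numeric enzyme stops are written only from Week 52.
- That INR and eosinophils are never rechecked. Scheduled hematology continues, and INR may return with a restarted work-up.
- That sites do not run these tests in practice. The contents of the retest kit and the laboratory manual are not shown, so the point concerns only what item 2 orders.

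**Conclusion.** The point holds from Week 52 onward: the follow-up draws that justify continued dosing do not order two of the tests on which mandatory stops depend. It is a minor but worthwhile safety correction.

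The exposed group is narrow. It comprises asymptomatic subjects still on or resuming drug at 3-5x ULN, or at 5-8x ULN for up to 2 weeks after Week 64, with bilirubin no higher than 2x ULN. They must also have passed INR and eosinophils at the work-up and crossed a threshold later. The draw counts assume that Table 1 is followed at its minimum frequency and that, for the count between visits, one weekly draw coincides with each scheduled visit. The number of subjects affected cannot be derived, and no bias in the study's safety summaries is claimed.

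**What to change.** In Attachment 1, item 2, add INR and hematology with differential to each Table 1 draw while ALT/AST is >=3x ULN in subjects still on or resuming drug from Week 52. Align the retest kit and laboratory manual if they do not already carry these tests. Leave every threshold and every Table 1 frequency as it is.

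The cost is one line of text and two tubes on draws already being made. The volume counts against the 450 mL yearly cap (Section 9.1.1). The protocol gives no tube sizes, so 4-7 mL per draw is an assumption:

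- 1-2 draws: 1 x 4 = 4 to 2 x 7 = 14 mL (0.9-3.1% of 450)
- 3-4 draws: 3 x 4 = 12 to 4 x 7 = 28 mL (2.7-6.2%)
- 12 weekly draws: 12 x 4 = 48 to 12 x 7 = 84 mL (10.7-18.7%)

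The room left under the cap is unknown, because per-subject volumes are in the laboratory manual. More frequent differentials may also bring some stops and serious adverse event reports from unrelated eosinophil rises, such as allergy. Restarting drug then needs agreement between sponsor and site (Section 10.2). That follows from the existing 5% threshold.
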